Inclusion/Exclusion criteria ^g	X	X						
Evaluate presence of SpA features	X	X						
Randomization		X						
Concomitant medications	X	X	X	X	X	X	X	X
NSAID use	X	X	X	X	X	X	X	X
Preexisting conditions and medical history ^h	X	X	X	X	X	X	X	X
Adverse events	X	X	X	X	X	X	X	X
Eye symptom assessment ⁱ	X	X	X	X	X	X	X	X
Dispense IP		X			X	X	X	X
Administer IP on site ^j		X						X
IP compliance ^k					X	X	X	X
Dispense SDAL		X			X	X	X	X

	Screening (Period 1)	Baseline Randomization	Blinded Treatment Dosing Period (Period 2) ^a					
CRF Visit (V) Number	V1	V2	V3	V4	V5	V6	V7	V8
Weeks Since Randomization		W0	W1	W2	W4	W8	W12	W16
Study Days	Up to -42 d	0	7 ± 2d	14 ± 2d	28 ± 2d	56 ± 4d	84 ± 4d	112 ± 4d
Collect, review, and enter data from SDAL		X			X	X	X	X
Clinical Efficacy/Health Outcomes								
MRI of spine and SIJ ^x	X ^y							X ^z
X-ray of the spine ^{cc}	X							
X-ray of the SIJ ¹	X							
Linear BASMI		X				X		X
Chest expansion		X				X		X
Occiput to wall distance		X				X		X
Enthesitis MASES		X				X		X
Patient Global Assessment of Disease Activity NRS	X	X	X	X	X	X	X	X
Spinal pain	X	X	X	X	X	X	X	X
BASFI	X	X	X	X	X	X	X	X
BASDAI	X	X	X	X	X	X	X	X
C-SSRS ^m	X	X	X	X	X	X	X	X
Self-Harm Supplement Form ^m	X	X	X	X	X	X	X	X
FACIT Fatigue Scale	X	X				X		X
SF-36	X	X			X	X		X
ASAS HI	X	X			X	X		X
QIDS-SR16	X	X						X
EQ-5D-5L		X						X
WPAI-SpA		X						X
Laboratory Tests								
HLA-B27 ⁿ	X							
CRP	X ^o	X	X	X	X	X	X	X
Administer PPD/Collect QuantiFERON®-TB Gold/ T-SPOT® ^p	X							

	Screening (Period 1)	Baseline Randomization	Blinded Treatment Dosing Period (Period 2) ^a					
CRF Visit (V) Number	V1	V2	V3	V4	V5	V6	V7	V8
Weeks Since Randomization		W0	W1	W2	W4	W8	W12	W16
Study Days	Up to -42 d	0	7 ± 2d	14 ± 2d	28 ± 2d	56 ± 4d	84 ± 4d	112 ± 4d
ECG	X							
FSH ^d	X							
HIV/HCV	X							
HBV ^e	X ^f	X ^f					X ^f	
Serum pregnancy test ^g	X							
Urine pregnancy test ^g		X	X	X	X	X	X	X
Serum chemistry	X	X			X	X	X	X
PTT, PT/INR	X							X
Lipid panel (fasting) ^h		X						X
Hematology	X	X			X	X	X	X
Urinalysis	X							X
TSH and free T4	X							
Immunogenicity testing ^u		X	X	X	X	X	X	X
PK sampling ^{u,v}		X	X	X	X	X	X	X

	Extended Treatment Period (Period 3) ^a									ETV
CRF Visit (V) Number	V9	V10	V11	V12	V13	V14	V15	V16	V17	ETV
Weeks Since Randomization	W20	W24	W28	W32	W36	W40	W44	W48	W52	
Study Days	140 ± 4d	168 ± 4d	196 ± 4d	224 ± 4d	252 ± 4d	280 ± 4d	308 ± 4d	336 ± 4d	364 ± 4d	
Physical examination ^c									X	X
Vital signs (BP and pulse) ^d	X	X	X	X	X	X	X	X	X	X

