Weight ^{aa}	X	X	X	X	X	X	X	X	X	X
Concomitant medications	X	X	X	X	X	X	X	X	X	X
NSAID use	X	X	X	X	X	X	X	X	X	X
Preexisting conditions and medical history ^h	X	X	X	X	X	X	X	X	X	X
Adverse events	X	X	X	X	X	X	X	X	X	X
Eye symptom assessment ⁱ	X	X	X	X	X	X	X	X	X	X
Dispense IP	X	X	X	X	X	X	X	X		
IP compliance ^k	X	X	X	X	X	X	X	X	X	X
Dispense SDAL	X	X	X	X	X	X	X	X		
Collect, review, and enter data from SDAL	X	X	X	X	X	X	X	X	X	X
Clinical Efficacy/Health Outcomes										
MRI of spine and SIJ ^x									X ^{bb}	X ^z
Linear BASMI		X			X				X	X
Chest expansion		X			X				X	X
Occiput to wall distance		X			X				X	X
Enthesitis MASES		X			X				X	X
Patient Global Assessment of Disease Activity NRS	X	X	X	X	X	X	X	X	X	X
Spinal Pain	X	X	X	X	X	X	X	X	X	X
BASFI	X	X	X	X	X	X	X	X	X	X
BASDAI	X	X	X	X	X	X	X	X	X	X

	Extended Treatment Period (Period 3) ^a									ETV
CRF Visit (V) Number	V9	V10	V11	V12	V13	V14	V15	V16	V17	ETV
Weeks Since Randomization	W20	W24	W28	W32	W36	W40	W44	W48	W52	
Study Days	140 ± 4d	168 ± 4d	196 ± 4d	224 ± 4d	252 ± 4d	280 ± 4d	308 ± 4d	336 ± 4d	364 ± 4d	
C-SSRS ^m	X	X	X	X	X	X	X	X	X	X
Self-Harm Supplement Form ^m	X	X	X	X	X	X	X	X	X	X
FACIT Fatigue Scale					X				X	X
SF-36					X				X	X
ASAS HI					X				X	X
QIDS-SR16					X				X	X
EQ-5D-5L									X	X
WPAI-SpA									X	X
Laboratory Tests										
CRP	X	X	X	X	X	X	X	X	X	X
HBV ^f		X ^f			X ^f		X ^f		X ^f	X ^f
Urine pregnancy test ⁵	X	X	X	X	X	X	X	X	X	X
Serum chemistry	X	X	X	X	X		X		X	X
PTT, PT/INR		X			X				X	
Lipid panel (fasting) ^t		X			X				X	
Hematology	X	X	X	X	X		X		X	X
Urinalysis		X			X				X	X
Immunogenicity testing ^u		X			X				X	X
PK sampling ^{u,v}		X			X				X	X

	Post-Treatment Follow-Up for Patients Discontinuing Treatment (Period 4) ^w	
	Required Follow-Up Visits	
CRF V (visit) number	V801	V802
Study Weeks	LV + 4W	LV + 12W
Study Days	±14d	±14d
Concomitant medications	X	X
Vital signs (BP and pulse) ^d	X	X
Weight ^{aa}	X	X
Preexisting conditions and medical history ^h	X	X
Adverse events	X	X
C-SSRS ^m	X	X
Self-Harm Supplement Form ^m	X	X
HBV ^f	X ^f	X ^f
Serum chemistry	X	X
Hematology	X	X
Immunogenicity testing ^u	X	X
PK sampling ^{u,v}	X	X

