Appendix 2. Clinical Laboratory Tests

Clinical Safety Laboratory Tests to be Performed by Sponsor-Designated Laboratory

Hematology ^a :	Serum Chemistry ^a :
Hemoglobin	Sodium
Hematocrit	Potassium
Erythrocyte count (RBC)	Bicarbonate
Mean cell volume (MCV)	Chloride
Mean cell hemoglobin concentration (MCHC)	Phosphorus
Leukocytes (WBC)	Total bilirubin
Platelets	Direct bilirubin
Absolute counts of:	Alkaline phosphatase
Neutrophils, segmented	Alanine aminotransferase (ALT/SGPT)
Neutrophils, juvenile (bands)	Aspartate aminotransferase (AST/SGOT)
Lymphocytes	Blood urea nitrogen (BUN)
Monocytes	Uric acid
Eosinophils	Creatinine
Basophils	Calcium
Urinalysis (dipstick)^a:	Glucose
Color	Albumin
Specific gravity	Cholesterol (total)
pH	Total protein
Protein	Calculated creatinine clearance ^b
Glucose	Creatine phosphokinase (CPK)
Ketones	Triglycerides
Bilirubin	Gamma-glutamyl transferase (GGT)
Urobilinogen	Lipid Panel:
Blood	Low density lipoprotein (LDL)
Nitrite	High density lipoprotein (HDL)
Urine creatinine	Very low density lipoprotein (VLDL)
Leukocyte esterase	
Other Tests:	
Human immunodeficiency virus antibody (HIV) ^f	Pregnancy test (serum) ^d
Hepatitis B surface antigen (HBsAg) ^f	Follicle-stimulating hormone (FSH) ^e
Anti-hepatitis B surface antibody (HBsAb) ^f	Thyroid-stimulating hormone (TSH) and free T4
Anti-hepatitis B core antibody (HBcAb) ^f	Ixekizumab serum concentration (pharmacokinetic [PK])
Anti-hepatitis C antibody ^{f,h}	Partial thromboplastin time (PTT)
HBV DNA ^g	Prothrombin time/international normalized ratio (PT/INR)
High sensitivity C-reactive protein (CRP)	Immunogenicity testing (anti-ixekizumab Ab)
Purified protein derivative (PPD) ⁱ	
Urine pregnancy test ^d (assayed by clinical study site)	
QuantiFERON®-TB Gold test ⁱ	
T-SPOT® ⁱ	
HLA-B27	

Abbreviations: Ab = antibody; DNA = deoxyribonucleic acid; HBV = hepatitis B virus; mRNA = messenger ribonucleic acid; RBC = red blood cells; SGOT = serum glutamic oxaloacetic transaminase; SGPT = serum glutamic pyruvic transaminase; T4 = thyroxine; WBC = white blood cells.

- a Unscheduled blood chemistry, hematology, and urinalysis panels may be performed at the discretion of the investigator.
- b Cockcroft-Gault calculation is used for the calculated creatinine clearance.
- c For the fasting lipid profile, patients are not to eat or drink anything except water for 12 hours prior to test. Fasting is not required for the screening visit (Visit 1).

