6.11.4. Clinical Laboratory Evaluation

Clinical laboratory assessments include hematology, serum chemistry, urinalysis, and safety-related immune markers such as neutrophil counts. All laboratory tests will be presented using the international system of unit (SI) when applicable.

Continuous laboratory tests will be summarized as changes from baseline to last observation for patients who have both baseline and at least one postbaseline result for Period 2 and 3, respectively:

- The scheduled visits/measurements will be included. The unscheduled visits and the repeat measurements will be excluded.
- For the Safety Population for Period 2, the comparisons between treatment groups will be conducted using an ANCOVA with treatment group and baseline value in the model.
- Data will be analyzed based on original scale.

Laboratory test observed values at each visit (starting at baseline) and change from baseline to each scheduled visit, respectively, will be displayed in box plots for patients who have both a baseline and at least one postbaseline result. These box plots will be used to evaluate trends over time and to assess a potential impact of outliers on central tendency summaries.

- The scheduled visits/measurements will be included. The unscheduled visits and the repeat measurements will be excluded.
- The following summary statistics will be included as a table below the box plot: number of patients with a baseline and at least one postbaseline result, mean, standard deviation, minimum, Q1, median, Q3, and maximum.
- Data will be summarized based on original scale.
- On the box plots of the laboratory test observed values, the lines of the reference ranges/limits (by using the performing laboratory reference ranges) will be added. In cases where limits vary across age and gender, the lowest of the high limits and the highest of the low limits will be used.

The number and percentage of patients with a treatment-emergent or follow-up emergent abnormal, high, or low for laboratory tests will be summarized by treatment group for each study period (Period 2 or 3 or 4). The comparisons between treatment groups will be conducted using Fisher's exact test for the Safety Population for Period 2.

- All scheduled, unscheduled and repeated measurements will be included.

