- Performing laboratory will be used to defined the low and high limits reference ranges except for leukocyte, neutrophil, lymphocyte and platelet counts, where Lilly defined lower limit of normal will be used for these 4 labs.
- Alanine aminotransferase (ALT), aspartate aminotransferase (AST), total bilirubin, alkaline phosphatase (ALP), neutrophils, leukocytes, platelets, and lymphocytes will not be included in the treatment-emergent abnormal, high, or low summary as a separate analysis addressing the risk of liver injury is described in Section 6.11.3.1 and a separate analysis addressing Leukocytes (WBC) and Platelets is described in Section 6.11.4.1.
- Note that the ranges are defined by a lower limit of normal (LLN) and an upper limit of normal (ULN). A result that is greater than or equal to the LLN and less than or equal to the ULN is considered to be within the normal ranges.
- For categorical laboratory tests:
 - Treatment-emergent abnormal value is defined as a change from normal at all baseline visits to abnormal at any time postbaseline during the treatment period.
 - Follow-up emergent abnormal result is defined as a change from normal at baseline to abnormal at any time during the follow-up period.
- For continuous laboratory tests:
 - Treatment-emergent high value is defined as a change from a value less than or equal to the ULN at all baseline visits to a value greater than the ULN at any time postbaseline during the treatment period.
 - Treatment-emergent low value is defined as a change from a value greater than or equal to the LLN at all baseline visits to a value less than the LLN at any time postbaseline during the treatment period.
 - Follow-up emergent high value is defined as a change from a value less than or equal to the ULN at baseline to a value greater than the ULN at any time postbaseline during the follow-up period.
 - Follow-up emergent low value is defined as a change from a value greater than or equal to the LLN at baseline to a value less than the LLN at any time postbaseline during the follow-up period.
 - By-patient listing of abnormal laboratory test results (criteria defined in the shift tables excluding the normal category) for parameters of special interest (hepatic, leukocytes and platelets) will be provided.

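### By-visit plots and treatment-emergent highs for glucose, triglycerides and total cholesterol mix fasting samples with samples for which no fast is required

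*Protocol*

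**What the plan says.** Protocol Appendix 2 places glucose, total cholesterol and triglycerides under Serum Chemistry. Its Lipid Panel holds only LDL, HDL and VLDL. The 12-hour rule is worded for the lipid profile: "For the fasting lipid profile, patients are not to eat or drink anything except water for 12 hours prior to test". A Schedule of Activities footnote (Protocol Section 2) repeats it. The Appendix 2 footnote adds that fasting is not required at Visit 1.

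The Schedule draws serum chemistry at Visit 1, Week 0, Weeks 4, 8, 12 and 16, Weeks 20, 24, 28, 32, 36, 44 and 52, the early termination visit (ETV), and both follow-up visits. The fasting lipid panel is scheduled only at Weeks 0, 16, 24, 36 and 52.

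SAP 6.11.4 uses these data in three ways:
- Continuous tests are summarised as change from baseline to last scheduled observation, with ANCOVA in Period 2.
- Observed values and changes are shown in box plots at every scheduled visit, with a statistics table beneath. Their purpose is stated: "These box plots will be used to evaluate trends over time and to assess a potential impact of outliers on central tendency summaries".
- A treatment-emergent high is a move from at or below the upper limit of normal (ULN) at all baseline visits "to a value greater than the ULN at any time postbaseline during the treatment period". Scheduled, unscheduled and repeat values all count.

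The tests that SAP 6.11.4 leaves out of the treatment-emergent summary are liver tests and blood counts, so these three analytes stay in. The SAP does not mention fasting state.

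**The concern.** Triglycerides and glucose depend on recent food intake; total cholesterol is the lesser concern. If patients fast at Week 0, need not fast at Weeks 4 to 12, and fast again at Week 16, the box plots can rise and fall because of the sampling rule alone. A plot meant to reveal time trends would then show one that is not a drug effect.

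An any-time definition of a high picks up every after-meal value. In Period 3 the safety baseline is usually the fasting Week 16 value, most of the later draws carry no fasting requirement, and there is no between-group comparison to absorb the artefact. The reported Period 3 rates of high triglycerides or glucose could therefore look like a consequence of longer ixekizumab exposure.

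**Working it through.** **Step 1: visit counts from the Schedule of Activities.** The documents state no figure for this point, so there is none to reproduce.

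| Period | Postbaseline chemistry visits | Also lipid-panel visits | No fast stated |
|---|---|---|---|
| 2 | Weeks 4, 8, 12, 16 (4) | Week 16 (1) | 3 of 4 |
| 3 | Weeks 20, 24, 28, 32, 36, 44, 52 (7) | Weeks 24, 36, 52 (3) | 4 of 7 |
| Total | 11 | 4 | 7 of 11 (64%) |

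The ETV and the two follow-up visits draw chemistry without a lipid panel and are outside these counts.

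**Step 2: which analyses are affected.**
- *Change to last observation.* In completers this runs from Week 0 to Week 16 in Period 2, and from Week 16 (the Period 3 safety baseline in most cases, SAP 6.1.2) to Week 52 in Period 3. All are lipid-panel visits. Only patients whose last scheduled value falls at another visit or the ETV are affected.
- *By-visit box plots.* Affected in both periods.
- *Treatment-emergent highs, Period 2.* The baseline is all results from Visit 1 to first injection (SAP 6.1.1 and 6.11), so it includes Visit 1, where no fast is required. A patient already high there cannot count as treatment-emergent. This reduces the mismatch but does not remove it.
- *Treatment-emergent highs, Period 3.* The baseline is usually the single fasting Week 16 value, set against 4 of 7 draws with no fast stated. This is the clearest case.

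**Step 3: illustration of size.** The documents give no rates, so these are assumptions. In a patient normal at baseline, the chance of a value above the ULN is f = 5% per fasting draw and n = 10% to 20% per non-fasting draw, with independent draws. With a fasting and b non-fasting draws,

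P(any high) = 1 − (1 − f)^a × (1 − n)^b.

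- Period 2 as scheduled (a = 1, b = 3): 1 − 0.95 × 0.90³ = 30.7%; 1 − 0.95 × 0.80³ = 51.4%.
- Period 2, same four draws all fasting: 1 − 0.95⁴ = 18.5%.
- Period 3 as scheduled (a = 3, b = 4): 1 − 0.95³ × 0.90⁴ = 43.7%; 1 − 0.95³ × 0.80⁴ = 64.9%.
- Period 3, same seven draws all fasting: 1 − 0.95⁷ = 30.2%.

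With the number of draws held fixed, lack of fasting adds about 12 to 33 percentage points in Period 2 and 14 to 35 in Period 3.

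**The case against.** A reader might infer that the laboratory change analyses in general compare fasting with non-fasting samples. The documents do not support that: the change tabulated in both periods, and tested in Period 2, is to last observation, which in completers is fasting to fasting.

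A reader might also infer that the Period 2 treatment comparison is biased. It is not. Both arms follow the same schedule, so background highs rise in both. The most that follows is dilution, and four draws also give more chances of detection than one.

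It is tempting to set the all-visit rate against the rate from fasting draws only, which on the same assumptions is 5% in Period 2 and 1 − 0.95³ = 14.3% in Period 3. That overstates the point. At the lower assumed rate, more than half of each gap comes from counting more draws: 18.5 − 5 = 13.5 of 30.7 − 5 = 25.7 points, and 30.2 − 14.3 = 15.9 of 43.7 − 14.3 = 29.4 points.

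The reach of the fasting rule is itself uncertain. The Appendix 2 footnote exempts Visit 1, yet no lipid panel is scheduled there while chemistry is, so the rule may have been meant to cover the chemistry lipids. The footnote's marker is not visible in the extracted table, which may be an extraction loss. Protocol 9.4.3 also refers sites to a central laboratory manual not available here. The absence of a stated fast does not show that patients ate. This stands, and is why the claim is only that the samples may be non-fasting. Lipids and glucose are also not among the adverse events of special interest.

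**Conclusion.** The point holds in limited form. No fast is stated at 7 of 11 scheduled postbaseline treatment visits where these analytes are drawn, and SAP 6.11.4 neither separates nor flags samples by fasting state. The by-visit box plots, and the treatment-emergent highs chiefly in Period 3, therefore mix fasting and possibly non-fasting samples. The visit counts come directly from the Schedule. The size of the effect on rates is illustrative: it rests on assumed per-draw probabilities, on independence between draws, and on patients not fasting where no fast is required. This is a minor matter for the trial's conclusions, but it can make a safety display misleading and is cheap to correct.

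**What to change.** In SAP 6.11.4, for triglycerides and glucose, and for total cholesterol for consistency:

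1. Draw the by-visit box plots and the tables beneath them on lipid-panel visits only: Weeks 0 and 16 for Period 2, and Weeks 16 (baseline), 24, 36 and 52 for Period 3.
2. Add a treatment-emergent-high summary limited to lipid-panel visits, with Week 0 as baseline for Period 2 and Week 16 for Period 3. Present it beside the all-visit summary.

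Keep the all-visit summary. The ETV has no lipid panel, so limiting everything to lipid-panel visits would remove all scheduled postbaseline values for patients who leave before Week 16, and would drop 7 of 11 visits from a safety screen.

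In the protocol, state whether the Appendix 2 fasting footnote, including its Visit 1 exemption, covers the chemistry analytes.

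Cost: a short SAP addition, a visit filter, one extra table and fewer time points in the plots. No new visits or samples are needed.

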Appendix 3. Study Governance Considerations

Appendix 3.1. Regulatory and Ethical Considerations, Including the Informed Consent Process

Appendix 3.1.1. Informed Consent

The investigator is responsible for:

- ensuring that the patient understands the nature of the study, the potential risks and benefits of participating in the study, and that their participation is voluntary.
- ensuring that informed consent is given by each patient or legal representative. This includes obtaining the appropriate signatures and dates on the ICF prior to the performance of any protocol procedures and prior to the administration of investigational product.
- answering any questions the patient may have throughout the study and sharing in a timely manner any new information that may be relevant to the patient's willingness to continue his or her participation in the study.
- ensuring that a copy of the ICF is provided to the participant or the participant's legal representative and is kept on file.
- ensuring that the medical record includes a statement that written informed consent was obtained before the participant was enrolled in the study and the date the written consent was obtained. The authorized person obtaining the informed consent must also sign the ICF.

Appendix 3.1.2. Ethical Review

The investigator must give assurance that the ERB was properly constituted and convened as required by International Conference on Harmonisation (ICH) guidelines and other applicable laws and regulations.

Documentation of ERB approval of the protocol and the ICF must be provided to Lilly before the study may begin at the investigative site(s). Lilly or its representatives must approve the ICF, including any changes made by the ERBs, before it is used at the investigative site(s). All ICFs must be compliant with the ICH guideline on GCP.

The study site's ERB(s) should be provided with the following:

- the protocol and related amendments and addenda, current IB and updates during the course of the study
- ICF
- other relevant documents (for example, curricula vitae, advertisements)

Appendix 3.1.3. Regulatory Considerations

This study will be conducted in accordance with the protocol and with the:

- consensus ethics principles derived from international ethics guidelines, including the Declaration of Helsinki and Council for International Organizations of Medical Sciences (CIOMS) International Ethical Guidelines
- applicable ICH GCP Guidelines
- applicable laws and regulations

Some of the obligations of the sponsor will be assigned to a third-party.

Appendix 3.1.4. Investigator Information

Physicians with a specialty in rheumatology will participate as investigators in this clinical trial.

Appendix 3.1.5. Protocol Signatures

The sponsor's responsible medical officer will approve the protocol, confirming that, to the best of his or her knowledge, the protocol accurately describes the planned design and conduct of the study.

After reading the protocol, each principal investigator will sign the protocol signature page and send a copy of the signed page to a Lilly representative.

Appendix 3.1.6. Final Report Signature

The CSR coordinating investigator will sign the final CSR for this study, indicating agreement that, to the best of his or her knowledge, the report accurately describes the conduct and results of the study.

The CSR coordinating investigator will be selected by the sponsor. If this investigator is unable to fulfill this function, another investigator will be chosen by Lilly to serve as the CSR coordinating investigator.

The sponsor's responsible medical officer and statistician will approve the final CSR for this study, confirming that, to the best of his or her knowledge, the report accurately describes the conduct and results of the study.

Appendix 3.2. Data Quality Assurance

To ensure accurate, complete, and reliable data, Lilly or its representatives will do the following:

- provide instructional material to the study sites, as appropriate.
- sponsor start-up training to instruct the investigators and study coordinators. This training will give instruction on the protocol, the completion of the CRFs, and study procedures.
- make periodic visits to the study site.

- be available for consultation and stay in contact with the study site personnel by mail, telephone, and/or fax.
- review and evaluate CRF data and use standard computer edits to detect errors in data collection.
- conduct a quality review of the database.

In addition, Lilly or its representatives will periodically check a sample of the patient data recorded against source documents at the study site. The study may be audited by Lilly or its representatives, and/or regulatory agencies at any time. Investigators will be given notice before an audit occurs.

The investigator will keep records of all original source data. This might include laboratory tests, medical records, and clinical notes. If requested, the investigator will provide the sponsor, applicable regulatory agencies, and applicable ERBs with direct access to original source documents.

